## Aim 2: Distinguish between latent versus active PSSP using US shear strain mapping in the paretic compared with the non-paretic muscles.

**(c) US Shear Strain Mapping:** We will use the Bimanual Arm Trainer to passively move the shoulder repeatedly into ER at a steady rate set by a metronome (**Figure 9, unimanual mode**).

This has the advantage of creating a reproducible rate and amplitude of input motion which is difficult to achieve otherwise. The movement can be performed by moving the trough for one arm which is transduced to the other arm. The subject will be

**Figure 9.** The Bimanual Arm Trainer is an FDA-cleared device that facilitates rate controlled passive shoulder ER-ROM on the paretic side for shear strain mapping, as well as for precise assessment of pain-free shoulder ER-ROM before and after treatment for Aim 3.

positioned in a seated position as shown in **Figure 9B** so that the infraspinatus muscle is accessible from the back, and the pectoralis major muscle will be accessible from the front. The skin over the muscles will be marked and the transducer will be stabilized so that the tissues are not compressed at any time. Shoulder ER will be performed repeatedly at 0.5 Hz starting from a position of internal rotation with a range of 30° excursion for each cycle. This is ~1/3rd of the full range of motion and will bring the forearm into neutral position. During this motion, we will collect an ultrasound cine-loop, sampled at 1 Hz over a 30 second period also using the scanner system used in Aim 1.

Date: August 28, 2023

Principal Investigator: [name]

Application Number: IRB00354876

**US Data Processing:** US data acquired from the non-paretic and paretic sides will be processed with a custom program written in Matlab (Natick, MA). Tissue displacements between successive US frames will be estimated from the “raw” US radio frequency (RF) data using cross-correlation techniques [101, 102] with a 1 mm window incremented with a 90% overlap. The term “US frame” refers to the RF data acquired at each time point in the cine-loop. Tissue lateral displacement will be computed for each successive pair of US frames in a  $1 \times 1.5$  cm ROI centered laterally on the midpoint of the image. To visually document the presence of a shear plane within the muscle, we will generate successive displacement maps as a spatial representation of the displacement within the ROI for each pair of US frames. Corresponding cumulative lateral displacement maps will be obtained by summing tissue displacements over time. To calculate the magnitude of shear deformation at a standardized location across subjects, we will use a reference echolucent plane that is relatively stable during the movement and define sub-ROIs each  $2 \text{ mm} \times 10 \text{ mm}$  for analysis. The maximum shear strain in the sub-ROIs will be averaged and used for statistical analysis.

**US Data Analysis:** The mean values and standard deviations of the maximum shear strain will be obtained from the defined regions of interest in the pectoralis major and infraspinatus muscles and will be compared for latent and active PSSP on the paretic and non-paretic sides using mixed model analysis, as described above for Aim 1. We will use Pearson’s correlations to correlate the clinical and imaging measures.

**Expected results, potential pitfalls & solutions:** We expect that the mean maximum shear strain will be statistically significant between the healthy (non-paretic) and paretic latent and active PSSP groups to proceed to the R33 phase. We will have twice as much data for the non-paretic arm than for the latent and active PSSP groups. Since some subjects with stroke may not have perfectly healthy non-paretic sides, we will use the data from the healthiest subjects based on their clinical testing, which may provide a greater separation between these groups. ***The quantitative US data will be collected and analyzed in collaboration with Co-I [name] at Johns Hopkins with Co-I [name] at George Mason University.***

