### **Imaging Myofascial Dysfunction and Differentiating Latent and Active Pain Using**

**Quantitative US.** The relationship of abnormal HA accumulation in muscle to pain is likely to be dependent on muscle use. An MRI study of 89 patients with chronic PSSP showed that 35% of subjects exhibited a tear, and 53% of subjects exhibited tendinopathy of at least one rotator cuff, biceps or deltoid muscle. However, the tears and tendinopathies were not related to the severity of PSSP; instead, the degree of muscle atrophy was related to reduced severity of PSSP [13]. Since patients with PSSP also have greater motor impairment [12], they are likely to move it less, leading to more atrophy, and less pain. A study of the incidence and prevalence of PSSP among different regions of the world suggests that it is more prevalent in regions that offer more rehabilitation, suggesting that PSSP may be triggered by microtrauma during movement [73]. A stiff, shortened muscle is more likely to resist stretch, and become injured and inflamed during use. Shoulder pain during movement, especially during shoulder ER after stroke, predicts long term shoulder pain [74], suggesting that active PSSP is perhaps provoked by overuse of already dysfunctional, stiff shoulder muscles, making it distinguishable from latent PSSP.

Strain is the most commonly encountered muscle injury and characteristically occurs at the musculotendinous junction, where maximal stress accumulates, especially during eccentric (stretching) exercise [75]. The epimysium is continuous with the musculotendinous junction [76], and overuse injury is associated with accumulation of HA in the epimysium [21]. Since alteration in the viscoelastic properties of the accumulated HA can dramatically alter the shear plane motion [17], post-stroke muscle stiffness overlaid by overuse injury may cause greater shear dysfunction. However, the shear dysfunction and strain injury from microtrauma or overuse injury may not be detected using routine MRI or US [77, 78]. Shear strain can be quantified by US shear strain mapping -- a computational technique where a series of ultrasound images are acquired in rapid succession and cross correlation methods are used to quantify the relative mobility of layers within inter- and intramuscular fascia during motion [26]. Using this

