**(b) US Echo Texture Mapping:** Ultrasound imaging will be performed with an Alpinion E-CUBE12R US system (Seoul, South Korea) equipped with an L8-17 transducer with a frequency range of 8 to 17 MHz and a 20-mm width or the Clarius C3 Scanner HD (Vancouver, Canada) in the Motor Recovery Research Lab. The participant will be seated comfortably with the arm supported on an arm rest. The skin surface over the pectoralis major muscle will be marked with the muscle relaxed. All images were acquired with the same US system settings. The musculoskeletal imaging preset will be used with a 10-MHz center frequency, 3-cm depth, and 76-dB dynamic range. The pectoralis major muscle will be visualized in cross section at the location of the skin mark, and images will be acquired with the muscle relaxed, with the US transducer held steadily at the same anatomic location, in a direction perpendicular to the skin surface. Raw RF US data will be saved at a sampling frequency of 40 mega-samples/s.

**US Data Processing:** The intensity of the raw RF US data will be calculated using the Hilbert transform. For each participant, a single B-mode image frame at rest will be selected. Two different types of analyses will be performed. First, we will create spatial parameter maps by estimating the statistical model parameters from the histogram of echo intensities within a moving rectangular window. The window size will be varied from 3 times the acoustic wavelength to 7 times the wavelength. Second, we will select the entire muscle as the ROI for estimating the model parameters. For this analysis, the muscle will be identified manually in the corresponding B-mode images, and the muscle boundary will be manually marked by identifying the hyperechoic fascia boundaries. The entire muscle will be considered the ROI for analysis, including all fascia interfaces inside the muscle boundaries. The backscattered intensities within this muscle ROI will be normalized by the maximum value within the ROI and analyzed as per the theoretical models described in [69].

**US Data Analysis:** The model parameters (signal to noise ratio (SNR), shape and rate of the single gamma distribution, and shape, rate, and mixture probability of the gamma distributions (for example, **Figure 8**) will be estimated from the muscle

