**c. Statistical plan including sample size justification and interim data analysis.**

We determined our sample size for the R61 Phase based on the more stringent sample size requirement for Aim 2, which will compare two independent groups, i.e., patients with latent PSSP vs. patients with active PSSP in the paretic arm. Because Aims 1 and 2 have different measurements, we present our power analysis in terms of standardized effect sizes (Cohen's d), which would be applicable to either measurement (26).

Langevin et al's data on shear strain mapping in patients with and without low back pain (LBP), showed that the shear strain was reduced in the LBP group ( $56.4\% \pm 3.1\%$ ) compared with the No-LBP group ( $70.2\% \pm 3.6\%$ ), i.e., an extremely large effect size of 3.8, suggesting that large effect sizes are biologically plausible.

The effect sizes in Bishop et al's follow up porcine study (83), showed equally large effect sizes comparing shear strain in control animals versus animals with restricted movement (similar to latent PSSP in our study), versus animals with restricted movement plus injury (similar to active PSSP in our study). We conservatively assume a Cohen's d of 1, which though large is not as large as the cited numbers. To detect a difference between latent PSSP versus active PSSP, a sample size of 17 per group is adequate for statistical significance at the 0.05 level with 80% power. For comparisons between paretic versus non-paretic shoulders, we expect greater power for within-person paired comparisons. However, conservatively assuming no advantage due to within-person correlations, we will also have 80% power to detect differences between latent PSSP versus healthy (non-paretic) shoulders and active PSSP versus healthy shoulders (non-paretic). Since we will be making multiple MRI and US measurements in a population that is disabled and in pain, it is possible that there will be some attrition. Hence accounting for 15% attrition, we will enroll 20 patients per latent PSSP and active PSSP group.

**Figure 10.** Overview of study design for the R61 Phase.

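### Aim 2 images a 0.5 Hz arm movement at 1 Hz, giving two frames per cycle, so the recorded excursion can lie anywhere from 0 to 30 degrees depending on when recording starts and how exactly the movement is paced

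*Combined protocol and SAP*

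**What the plan says.** Section 4a, Aim 2 (c) US Shear Strain Mapping, sets the movement: "Shoulder ER will be performed repeatedly at 0.5 Hz starting from a position of internal rotation", with 30 degrees of excursion per cycle, paced by a metronome on the Bimanual Arm Trainer. The stated benefit of the device is "This has the advantage of creating a reproducible rate and amplitude of input motion". For the imaging, "we will collect an ultrasound cine-loop, sampled at 1 Hz over a 30 second period".

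The US Data Processing paragraph that follows says what a frame is: the term "refers to the RF data acquired at each time point in the cine-loop". It then says how frames are used: "Tissue displacements between successive US frames will be estimated" by cross-correlation with a 1 mm window. The displacements are summed over time, and maximum shear strain, averaged over sub-regions, is the analysed value.

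Two other places bear on the point. Section 3 (Background) describes shear strain mapping as a technique in which "a series of ultrasound images are acquired in rapid succession". Aim 1 (b) says "Raw RF US data will be saved at a sampling frequency of 40 mega-samples/s", which is the digitisation rate of the echo signal within a frame, not the rate at which frames are taken.

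On sample size, Section 7c assumes Cohen's d = 1 and concludes that "a sample size of 17 per group is adequate for statistical significance at the 0.05 level with 80% power".

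**The concern.** At two frames per cycle, a perfectly reproducible arm movement does not give a reproducible recorded movement. What the images show depends on where in the cycle the first frame falls and on small departures from the metronome rate. The plan controls neither: it gives no trigger, no gating, no arm angle logged with each frame and no pacing tolerance. Starting from internal rotation describes the movement, not the moment at which image acquisition begins.

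Maximum shear strain is the Aim 2 primary outcome (Sections 4a and 7a). The sample size rests on it, and the Aim 2 expected-results paragraph ties a significant group difference in it to proceeding to the R33 phase. Error from this source has nothing to do with latent or active PSSP. Motion between frames was never recorded, so it cannot be recovered afterwards.

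**Working it through.** **Inputs from the documents.** Movement 0.5 Hz, 30 degrees per cycle; cine-loop 1 Hz for 30 s (Section 4a, Aim 2 (c)); d = 1, 17 per group, 0.05 level, 80% power, 15% attrition (Section 7c).

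**The plan's own figure.** A two-sided two-sample t-test at 0.05 with d = 1 and 80% power needs n = 16.7, so 17 per group (power 80.7% at 17). Then 17 / 0.85 = 20. The sample size reproduces and is not in dispute.

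**Frames per cycle.** 1 Hz / 0.5 Hz = 2. In 30 s there are 30 frames over 0.5 × 30 = 15 cycles. Successive frames are 1 s apart in a 2 s cycle, that is, half a cycle.

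**Visible excursion at the exact rate.** Assume sinusoidal motion, angle(t) = 15 × (1 − cos(πt)), with the first frame t0 seconds after a turning point. The frames alternate between two angles whose difference is 30 × |cos(πt0)|. For constant-speed motion and t0 up to 0.5 s, the difference is 30 × (1 − 2t0).

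| First frame, s after a turning point | Sinusoidal | Constant speed |
|---|---|---|
| 0 | 30 degrees | 30 degrees |
| 0.25 | 21 | 15 |
| 0.33 | 15 | 10 |
| 0.5 (mid-swing) | 0 | 0 |

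The zero does not depend on the waveform: for any continuous motion with a 2 s period, some start time puts frames 1 s apart at equal angles. Summing frame-to-frame displacements does not help, because the sum contains only positions that were sampled.

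With a uniformly random start, the mean of |cos| is 2/π = 0.64, so 0.64 × 30 = 19.1 degrees. The SD is about 9.2 degrees (CV 48%), and a third of recordings show less than half the excursion. For constant speed the mean is 15 degrees and the CV 58%.

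**Pacing.** A 1% rate error shifts the phase by 0.01 × 0.5 × 360 = 1.8 degrees of phase per second. In a sinusoidal recording that starts in phase, the frame-to-frame step then falls from 30.0 to 18.0 degrees within the 30 s.

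**Illustrative effect on power.** Assumptions not in the documents: random start phase, strain proportional to the peak-to-peak excursion seen over the 30 frames, one independent factor per subject, 17 per group, two-sided t-test. The d = 1 case uses a difference of 13.8 and an SD of 13.8. The cited case uses the low back pain figures in Section 7c (56.4 ± 3.1 and 70.2 ± 3.6). With no sampling error, power is about 80% and about 100%.

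| Rate error (SD of mean rate) | 0% | 1% | 2% | 5% |
|---|---|---|---|---|
| Sinusoidal: CV of excursion | 48% | 30% | 23% | 15% |
| Sinusoidal: power, d = 1 | 20% | 38% | 48% | 64% |
| Sinusoidal: power, cited | 24% | 53% | 73% | 93% |
| Constant speed: CV of excursion | 58% | 40% | 32% | 21% |
| Constant speed: power, d = 1 | 16% | 26% | 36% | 53% |
| Constant speed: power, cited | 17% | 32% | 48% | 79% |

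The d = 1 result depends on the scale chosen. Across the same four rate errors, sinusoidal power is 48 / 66 / 70 / 76% with difference and SD both 28, and 9 / 16 / 24 / 41% with both 7. With the correct mean rate but random timing error of SD 0.05 / 0.10 / 0.15 s per frame, sinusoidal power is 40 / 61 / 74% (d = 1) and 56 / 94 / 100% (cited).

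Best case: recording starts within 0.1 s of a turning point at the exact rate. The CV is then 1.5% (sinusoidal) or 6% (constant speed), and d = 1 power is 80% or 77%.

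**Smallest fraction of the excursion captured, over all start phases.**

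| Frames/s | Sinusoidal | Constant speed |
|---|---|---|
| 1 | 0% | 0% |
| 2 | 70.7% | 50% |
| 5 | 95.1% | 80% |
| 10 | 98.8% | 90% |
| 20 | 99.7% | 95% |

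**The case against.** The best reply is that 1 Hz is a slip. The Background describes rapid acquisition, and displacement maps for each pair of frames make little sense at two frames per cycle. If so, one corrected number removes the problem and no power is lost. That may well be true, but nothing in the documents corrects the figure, and an operator who follows the text would collect unusable phase information.

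The second reply is about size, and much of it stands. Section 7c plans on d = 1 after citing an effect of 3.8, and a standardised effect can already include measurement error, so adding phase error on top of d = 1 may count some noise twice. In the cited case several scenarios stay above 80%. Irregular pacing also helps, because a peak-to-peak value over 30 frames then catches more of the swing. For sinusoidal motion, a 2% rate error combined with 0.10 s of jitter gives a CV of 10% and power of 73% (d = 1) or about 100% (cited); 5% with 0.10 s gives 7%, 77% and about 100%. These combinations soften the loss, though d = 1 power still falls short of 80%, and constant-speed motion was not examined in combination.

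Third, the t-test used here is not the mixed model that compares non-paretic, latent and active shoulders, so these powers are not the chance of meeting the R33 condition. That is correct.

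None of this touches the two frames per cycle or the 0 to 30 degree range.

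**Conclusion.** The concern holds. As written, Aim 2 records two frames per movement cycle, and the visible excursion ranges from 0 to 30 degrees according to start phase and pacing. That follows from the plan's own rates; only the intermediate values depend on the assumed waveform.

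The loss of power is not established. It depends on pacing, synchronisation, waveform and the scale of strain, none of which the documents give. In the illustrations, d = 1 power runs from 9% to about 80%. Section 7c does not discuss this source of error, and any margin in d = 1 was not set with it in mind.

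Even with perfect synchronisation, each pair of frames would span the whole 30 degree sweep with nothing in between. Whether cross-correlation tracking with a 1 mm window holds over that step cannot be judged, because tissue displacement in millimetres is not given.

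This must be settled before Aim 2 data are collected: it affects a primary outcome and cannot be repaired afterwards.

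**What to change.** In Section 4a, Aim 2 (c), confirm or correct the 1 Hz figure. Replace it with a minimum cine frame rate well above the movement rate that both scanners allowed in Aim 1 (b) can save as raw RF data. About 20 frames/s would give 20 / 0.5 = 40 frames per cycle and 20 × 30 = 600 frames per recording. If storage does not allow that, 10 frames/s still captures at least 98.8% (sinusoidal) or 90% (constant speed) of the excursion.

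State whether recording is synchronised to arm position, and bring the Background description, the acquisition paragraph and the frame-to-frame processing paragraph into agreement. Optionally, compute maximum strain within each cycle and average over the 15 cycles.

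The change needs no extra patients or visits. Files grow from 30 to 600 frames per recording at 20 frames/s. The documents do not show that either scanner can save raw RF data at that rate for 30 s, so this must be tested on both before the minimum is fixed.

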## INNOVATION

This proposal is innovative in several ways:

**MR/US Imaging Innovation: T1 $\rho$  relaxation mapping of muscle will quantify GAG content in muscle non-invasively.** Direct methods using muscle biopsy and staining for HA are not ethical or practical to perform before and after injections in humans. Our research team has shown that it is feasible to use 3D-T1 $\rho$  to map GAG content in muscle in patients with stroke and myofascial dysfunction non-invasively [21-23], without the use of exogenous contrast agent injection or radiofrequency hardware modifications. In addition, we will correlate T1 $\rho$  relaxation times with statistical echo texture maps obtained using quantitative US to develop a clinic-friendly tool to infer extent of HA accumulation. These innovations will establish the pathophysiology of myofascial dysfunction in PSSP to enable appropriate treatment and monitoring.

**Quantitative US Innovation 2: Shear strain mapping has the potential to differentiate between latent pain and active pain in PSSP.** Movement restriction reduces shear strain measured using quantitative US in a porcine model of back pain. However, the combination of movement restriction and local injury leads to an additive, and quantifiable reduction in US shear strain [79], suggesting that US shear strain mapping may be able to differentiate latent PSSP (due to movement restriction alone) from active PSSP (due to a combination of movement restriction and local injury). Using this method in PSSP will enable the quantification of the underlying pathophysiology that leads to latent and active PSSP. This will enhance pain management to address the underlying pathophysiology rather than just provide symptomatic relief.

**Approach Innovation: We will use the Bimanual Arm Trainer (BAT) to provide passive shoulder ER and assess pain-free shoulder ER.** Several studies show a strong association between shoulder immobility and non-use, stiffness in the pectoralis major muscle, limitation in shoulder ER and PSSP [33-35] (Figure 6). We will use the BAT – an FDA-cleared device designed specifically to provide gentle, controlled passive ER-ROM (unimanual mode) at a fixed rate during shear strain mapping. For precise quantification of pain-free passive ER-ROM before and after treatment in the clinical trial, patients will use the non-paretic limb as the actuator (bimanual mode) enabling safe movements that are patient-controlled [80].

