## APPROACH

**Overview:** The primary objective of the R61 phase is to identify and develop quantitative measures that can differentiate abnormal myofascial tissues in latent versus active PSSP from relatively healthy tissues on the non-paretic side along with cross-sectional correlations with

clinical signs and symptoms. In addition, we will build the team to plan the R33 phase clinical trial during this first phase.

**Definition of latent PSSP:** The latent phase includes myofascial dysfunction, including soft tissue stiffness and non-painful reduction in ROM, which may be accompanied by focal palpable nodules that are tender to palpation. ***We will define latent PSSP as a difference of more than 10 degrees of passive ER-ROM between the non-paretic and paretic shoulders, with focal palpable nodules that may be tender on palpation with pain rating of <5/10*** [81].

**Definition of active PSSP:** During the active phase, the patient has painful reduction in ROM, spontaneous pain, and localized, tender indurated nodules on palpation of muscles that reproduces the local and/or radiating pain. Rajaratnam et al. found that a positive Neer test, which elicits pain on passive forward elevation of the arm with the scapula stabilized (**Figure 7A**), combined with the hand-behind-neck (HBN) maneuver eliciting a pain rating of  $\geq 5/10$  (**Figure 7B**), and a difference of more than 10 degrees of passive ER-ROM between the non-paretic and paretic shoulders has a 98% probability of predicting PSSP with 96.7% sensitivity and 99.0% specificity [81]. ***We will define active PSSP as a difference of more than 10 degrees of passive ER-ROM between the non-paretic and paretic shoulders, with focal palpable nodules that are tender on palpation, reproducing the pain, and eliciting a pain rating of  $\geq 5/10$  when combined with the HBN maneuver.***

**Figure 7.** Depiction of Neer test (A) and Hand-behind-neck (HBN) test (B) used to diagnose active PSSP (8).

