**Equation 1**

$$S = A \cdot e^{-TSL/T_{1\rho}} + A_0$$

**MRI Data Analysis:** The mean values and standard deviations of T1 $\rho$  relaxation times (ms) will be obtained from the defined regions of interest in the pectoralis major and infraspinatus muscles and will be compared on the paretic and non-paretic sides using mixed model analysis wherein the two sides are nested within one person, and healthy (non-paretic) versus latent PSSP versus active PSSP are examined as fixed effects. Prior to final analysis we will perform model diagnostics to assure that model assumptions regarding the fixed and random effects are met. The mean water and fat fractions of the muscles will also be obtained in percentages to quantify fat infiltration in the muscles, which will be used as predictors in the analysis. We will use Pearson's correlations to correlate the clinical and imaging measures.

**Expected results, potential pitfalls & solutions:** We expect an increase in T1 $\rho$  relaxation times in the paretic pectoralis major and infraspinatus muscles compared with the non-paretic side. We may also see a difference in location of the signal and/or relaxation times between latent and active PSSP. For example, subjects with active PSSP may show higher relaxation times in the

epimysial regions as seen with overuse injury, whereas subjects with latent PSSP may show higher relaxation times in the perimysial region. A two-compartment model of T1ρ mapping (bi-exponential model) can separate out the signal from the GAG content and the free water content of the ECM, and delineate a clearer picture of the extracellular environment of the muscle [23]. We can also analyze the data collected using this model, which may differentiate latent from active PSSP.

[figure not shown]
***All the MRI data will be collected and analyzed in collaboration with co-I [name] at Johns Hopkins in conjunction with [name] at NYU Langone.***

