## **7. Study Statistics**

**a. Primary outcome variable.**

This study has two primary outcomes. The first, which is the primary outcome for AIM 1, is to quantify the extent of HA accumulation using 3-D T1ρ MRI in both arms. The second, which is the primary outcome for AIM 2, is to use Quantitative Shear Stain Mapping to distinguish between latent and active PSSP on the paretic side compared with the non-paretic side.

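### Aim 2 sets out to distinguish latent from active PSSP, but no planned analysis estimates how well shear strain separates them, and the R33 condition rests on significance of means

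*Combined protocol and SAP*

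**What the plan says.** **The goal.** The Approach overview (Section 3) sets the R61 objective as to "identify and develop quantitative measures that can differentiate abnormal myofascial tissues in latent versus active PSSP", and the sentence goes on to contrast these with healthier tissue on the non-paretic side. Section 7a makes the Aim 2 primary outcome the use of shear strain mapping "to distinguish between latent and active PSSP on the paretic side compared with the non-paretic side". The Innovation text says: "Shear strain mapping has the potential to differentiate between latent pain and active pain in PSSP".

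**The hypothesis.** Section 2 words the Aim 2 hypothesis as an ordering: lowest shear strain in active PSSP, then latent, each taken relative to the non-paretic side.

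**The analysis.** Under Aim 2 in Section 4a, means and standard deviations of maximum shear strain in each muscle are obtained and "will be compared for latent and active PSSP on the paretic and non-paretic sides using mixed model analysis". The model is the one given for Aim 1, in which "healthy (non-paretic) versus latent PSSP versus active PSSP are examined as fixed effects". Pearson correlations with clinical measures are added.

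**The condition for R33.** The expected-results paragraph for Aim 2 says: "We expect that the mean maximum shear strain will be statistically significant between the healthy (non-paretic) and paretic latent and active PSSP groups", and makes this the basis for proceeding to R33.

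**The sample size.** Section 7c powers a difference in means between latent and active PSSP: Cohen's d of 1, 0.05 level, 80% power, 17 per group, raised to 20 for 15% attrition.

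**The concern.** A test of means asks whether two groups differ on average. Whether a measure distinguishes them depends on how much the distributions overlap, and a p-value does not report that. The plan contains no AUC, sensitivity, specificity, cut-off, overlap measure or minimum separation for latent versus active PSSP.

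The R33 sentence adds a second difficulty. It names the healthy side against the paretic latent and active groups. It can be read as a three-way comparison, or as two comparisons with the healthy side. On the second reading the condition could be met when latent and active PSSP do not differ at all, which would be an AUC of 0.50 for the contrast Aim 2 is about.

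At stake is what the R33 decision rests on. The phase could conclude that shear strain distinguishes latent from active pain with no planned figure showing how well it does so.

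**Working it through.** **Inputs.** From Section 7c: d = 1, level 0.05, power 80%, 17 evaluable and 20 enrolled per group. The document does not state sidedness; two-sided is assumed because it reproduces the figure.

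**Step 1: the plan's own number.** The noncentrality is d × √(n/2). Exact two-sided t-test power at d = 1 is 78.1% with 16 per group and 80.7% with 17, so 17 reproduces. A one-sided normal approximation gives 13 and does not fit. Attrition: 17 / (1 − 0.15) = 20.

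**Step 2: smallest significant observed difference, latent versus active.** d_min = t(0.975, 2n − 2) × √(2/n).
- n = 17: 2.037 × 0.343 = 0.70
- n = 20: 2.024 × 0.316 = 0.64

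**Step 3: what those differences mean for separation.** Assume two normal groups of equal variance and size. Then AUC = Φ(d/√2), and the misclassified share at the best single cut (the midpoint) is Φ(−d/2).

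| d | AUC | Misclassified |
|---|---|---|
| 0.64 (just significant, n = 20) | 0.67 | 37% |
| 0.70 (just significant, n = 17) | 0.69 | 36% |
| 1.00 (design value) | 0.76 | 31% |

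Misclassification exceeds one third only when d is below 2 × Φ⁻¹(2/3) = 0.86. Sensitivity and specificity both at 80% would need d = 2 × Φ⁻¹(0.80) = 1.68.

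**Step 4: precision of the AUC.** The Hanley-McNeil variance is [A(1 − A) + (n − 1)(Q1 − A²) + (n − 1)(Q2 − A²)] / n², with Q1 = A/(2 − A) and Q2 = 2A²/(1 + A). For A = 0.760 and n = 17, Q1 = 0.613, Q2 = 0.657 and A² = 0.578. The variance is (0.182 + 0.563 + 1.260)/289 = 0.0069, so SE = 0.083 and the 95% CI is 0.60 to 0.92. With n = 20 it is 0.61 to 0.91. For A = 0.69 and n = 17, SE = 0.092 and the CI is 0.51 to 0.87.

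**Step 5: how easily a modest marker passes.** With a true d of 0.70, the chance of p < 0.05 is 51% with 17 per group and 58% with 20.

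**The case against.** The strongest reply is that the protocol never promises to classify individual patients. The R61 objective speaks of tissues, and the Aim 2 hypothesis is an ordering of group levels that the three-state mixed model tests directly. Latent and active status are assigned clinically, and the impact statement stresses monitoring of treatment response, which a cross-sectional AUC does not measure. This stands in part: the analysis fits the hypothesis. It does not remove the gap between the analysis and the primary outcome, which is worded as distinguishing the two groups.

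A reader might infer that a p-value is the only output. The documents do not support that. Means, standard deviations and correlations are planned, and a rough d and AUC could be worked out from them afterwards. What is missing is a pre-specified estimate of separation with an interval, tied to the decision.

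A reader might also infer that a marker passing the test would typically misclassify more than a third of patients. That holds only for d below 0.86, and at the design value the share is 31%. In a simulation at a true d of 1 with 17 per group, about 19% of significant results had an observed d that low. If effects approach the 3.8 cited from the low back pain study, the AUC would be close to 1.

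Finally, the sample is too small for a precise AUC. That is true and is a reason to show the interval. The AUC need not carry a minimum value to be informative beside the p-value.

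**Conclusion.** The point holds as a gap in what the plan estimates, not as a wrong test. The mixed model answers whether shear strain is ordered across healthy, latent and active states. It does not estimate how well shear strain separates latent from active PSSP, and the only stated R33 condition neither asks for that nor clearly includes the contrast.

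With 17 per group, results from just significant to the design value correspond to AUC of about 0.69 to 0.76 and 36% to 31% misclassified. Significance is therefore compatible with modest separation.

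These figures are not in the documents. They assume normal data, equal variances, equal groups, one cut and one muscle, with d standardised on the scale analysed. A mixed model that draws error degrees of freedom from the non-paretic arms would lower the threshold d slightly. The change is cheap and worth making; the planned analysis does not need replacing.

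**What to change.** - Keep the mixed model and the sample size.
- State that the R33 criterion includes the active-versus-latent contrast.
- Pre-specify the AUC for active versus latent, using maximum shear strain on the paretic side relative to the same patient's non-paretic side. Say whether relative means a difference or a ratio.
- Give it for each muscle, or for one muscle named in advance, with a bootstrap 95% CI and no data-chosen cut-off.
- Make this the estimate behind any statement that shear strain distinguishes the groups, and report it beside the p-value in the R33 decision. Otherwise, limit the conclusion to a difference on average.

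The cost is one further analysis of data already collected. The downside is a wide interval, about ±0.16 at d = 1 with 17 per group, and a result that may look more modest than a significant p-value suggests.
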